6.3. Lifestyle Restrictions

6.3.1. Meals and Dietary Restrictions

Over the counter medications or supplements that are known to be strong inducers of CYP3A4, such as St John's Wort, should be discontinued for the duration of the study.

Except as stated above, participants should continue their regular diet for the duration of the study.

6.3.2. Caffeine, Alcohol, and Tobacco

For each visit, participants will abstain from any alcohol for 24 hours prior to the start of the visit until collection of the venous blood sample during each visit. For the duration of the study, participants should be encouraged to avoid excessive alcohol intake (defined as consumption of more than 1-2 drinks per day in the USA).

6.3.3. Activity

Participants should refrain from significant changes in their exercise level (e.g., joining a gym), except as instructed by the investigator, for the duration of the study. Participants will abstain from strenuous exercise, e.g. running, for 24 hours prior to each blood collection for clinical laboratory tests.

6.4. Screen Failures

Screen failures are defined as participants who consent to participate in the clinical trial but are never subsequently randomized. A minimal set of screen information is required to ensure transparent reporting of screen failure participants, meet the Consolidated Standards of Reporting Trials (CONSORT) publishing requirements, and respond to queries from Regulatory authorities. Minimal information includes demography, screen failure details, eligibility criteria, and any serious SAEs.

Participants are expected to meet study entry criteria when they are randomized. If a participant initially qualifies for the study and their condition changes prior to randomization such that they no longer qualify for the study, the participant should be considered a screen failure. Participants who experience a moderate/severe exacerbation of COPD in the period after the screening visit AND before the baseline visit should be considered a run-in failure, however these participants may be eligible for rescreening at a later date. Note: Participants who fail screen may be rescreened if, in the opinion of the investigator, the participant's condition was transient and the participant will qualify for the study at a later date during the study enrolment period. Participants may be rescreened a maximum of two times in total. Rescreened participants should be assigned a new participant number.

7. TREATMENTS

Study treatment is defined as any investigational treatment(s), marketed product(s), placebo, or medical device(s) intended to be administered to a study participant according to the study protocol.

7.1. Treatments Administered

Study Treatment Name:	GSK2881078	Placebo
Dosage formulation:	Capsule	Capsule
Unit dose strength(s):	0.5mg, 1.0mg	N/A

Dosage level(s)	1.0mg for women (2 x 0.5mg capsules) once daily 2.0mg for men (2x 1.0mg capsules) once daily	2 capsules once daily
Route of Administration	For oral use only	For oral use only
Dosing instructions:	Take as directed	Take as directed
Packaging and Labeling	Capsules will be provided in a bottle. Each bottle will be labeled as required per country requirement.	Capsules will be provided in a bottle. Each bottle will be labeled as required per country requirement.

7.1.1. Medical Devices

- There are no GSK manufactured medical devices (or devices manufactured for GSK by a third party) provided for use in this study.
- Other medical devices (not manufactured by or for GSK) provided for use in this study are the Actigraph physical activity monitor, a consumer pedometer and an android tablet which will be used to administer the home exercise program and electronic PROs.
- Instructions for medical device use are provided in the study reference manual.

7.2. Dose Modification

Not applicable.

7.3. Method of Treatment Assignment

Male and post-menopausal female participants who are between 50 and 75 years of age and meet all other study entry criteria will be assigned to one of the (Male: placebo or 2.0 mg of GSK2881078; Postmenopausal female: placebo or 1.0 mg of GSK2881078) in a ratio of 1:1 in accordance with the randomization schedule generated under the auspices of Clinical Statistics at GSK, prior to the start of the study, using validated software.

Separate randomizations will be generated for each gender, and the randomisation process will assign the container number for study treatment. Each participant will be dispensed blinded study treatment with unique container numbers, which will be distinct from the randomisation numbers.

If a participant experiences an exacerbation, then that participant may be replaced upon consultation with GSK. The replacement participant will receive the same treatment as the participant being replaced. The random number for the replacement participant will be 1000 + the random number for the replaced participant.

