7.4. Blinding

This will be a double blind (sponsor unblind) study and the following will apply.

- The investigator or treating physician may unblind a participant's treatment assignment **only in the case of an emergency** OR in the event of a serious medical condition when knowledge of the study treatment is essential for the appropriate clinical management or welfare of the participant as judged by the investigator.
- It is preferred (but not required) that the investigator first contacts the Medical Monitor or appropriate GSK study personnel to discuss options **before** unblinding the participant's treatment assignment.
- If GSK personnel are not contacted before the unblinding, the investigator must notify GSK as soon as possible after unblinding, but without revealing the treatment assignment of the unblinded participant, unless that information is important for the safety of participants currently in the study.
- The date and reason for the unblinding must be fully documented in the CRF

A participant will be withdrawn if the participant's treatment code is unblinded by the investigator or treating physician. The primary reason for discontinuation (the event or condition which led to the unblinding) will be recorded in the CRF.

- GSK's Global Clinical Safety and Pharmacovigilance (GCSP) staff may unblind the treatment assignment for any participant with an SAE. If the SAE requires that an expedited regulatory report be sent to one or more regulatory agencies, a copy of the report, identifying the participant's treatment assignment, may be sent to investigators in accordance with local regulations and/or GSK policy.
- Members of the GSK study team will be unblinded for in-stream data reviews and the interim analyses as appropriate. This may include the study statistician, programmers, physician project leader, Muscle Metabolism Discovery Performance Unit leader, safety review team and other decision makers. At the time of interim analysis, access to the randomization will be restricted to randomization numbers that have been assigned at the time of data cut-off.

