10.3.4. Interim Analyses

The Reporting and Analysis Plan will describe the planned interim analyses in greater detail.

In-Stream Review

Safety, tolerability, strength, lean mass, and functional endpoint data will be reviewed by the GSK study team on an ongoing basis throughout the study for the purpose of internal decision making. These reviews can include individual participant data, summaries by treatment group and graphical displays. GSK staff will be unblinded (See Section 7.3). Participants and all site personnel will be blinded to participant randomization.

Preliminary safety, strength, lean mass, functional endpoint and PK results may be reported prior to database freeze for the purposes of safety review by GSK and where required by regulatory bodies.

Interim Analysis

An interim analysis for the assessment of futility is planned. It is anticipated that a formal declaration of futility would not be made before at least 10 participants per group have completed dosing and all key study assessments. However, if at any time it is determined

that the probability of a successful outcome is sufficiently low, recruitment could be stopped. The primary endpoint for assessment of futility is strength. However, the decision to continue or stop recruitment will be made by the unblinded GSK clinical study team and SRT based on the evaluation of all available safety, efficacy, and tolerability data. Such decisions will be based on the totality of the data (including strength, lean mass, function, safety, and tolerability). The feasibility of making a decision to stop recruitment based on a futility analysis will be dependent on the recruitment rate. Whether recruitment is suspended for the interim analysis will be dependent on the recruitment rate. Assessment of futility will be done separately for female and male participants. A Bayesian predictive approach using a non-informative prior will be used to assess the futility of % change from baseline strength at 13 weeks.

The futility criteria for strength will be based on the posterior predictive probability at the interim that the end of study difference in % change from baseline strength between GSK2881078 and placebo will achieve a positive outcome ($\geq 9\%$). If the predicted probability of achieving this positive outcome is too low in the context of all available data, then enrolment into the treatment arm(s) or cohort may be stopped.

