## 12.7. Appendix 7: Reporting Standards for Missing Data

### 12.7.1. Premature Withdrawals

Element	Reporting Detail
General	
 
• Subject study completion (i.e. as specified in the protocol) was defined as subjects who completed all visits of the study including the follow-up visit.
 
• Withdrawn subjects may be replaced in the study.
 
• All available data from participants who were withdrawn from the study will be listed and all available planned data will be included in summary tables and figures, unless otherwise specified.
 
• Withdrawal visits will be assigned to a planned visit or an unscheduled visit and will be slotted as per Appendix 3: Assessment Windows.
 

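### Under Protocol 7.3, the replacement for a participant with an exacerbation inherits that participant's arm, and nothing requires the decision to replace to be made blind

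*Protocol*

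**What the plan says.** Protocol 7.3 provides a separate randomisation for each sex, with assignment "in a ratio of 1:1 in accordance with the randomization schedule generated under the auspices of Clinical Statistics at GSK". It then adds an exception: "If a participant experiences an exacerbation, then that participant may be replaced upon consultation with GSK". For that exception, "The replacement participant will receive the same treatment as the participant being replaced", and "The random number for the replacement participant will be 1000 + the random number for the replaced participant".

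Protocol 7.4 states: "Members of the GSK study team will be unblinded for in-stream data reviews and the interim analyses as appropriate". The roles it names as possibly unblinded include the statistician, the physician project leader and other decision makers. Protocol 10.3.4 allows the sponsor's team to look at individual participant data and summaries by treatment group on an ongoing basis, including strength. The same section protects the other side of the blind: "Participants and all site personnel will be blinded to participant randomization".

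Protocol 5.2 describes central 1:1 randomisation of at least 100 participants (25 per arm) to obtain about 80 evaluable (20 per arm). It allows extra enrolment if exacerbations and other early withdrawals together exceed about 20%. It does not mention inherited assignments.

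SAP 12.7.1 says: "Withdrawn subjects may be replaced in the study". SAP Section 4 places participants in the efficacy populations according to their randomised arm. The SAP plans no analysis that identifies or excludes replacements, and its table of changes from the protocol does not mention replacement.

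**The concern.** In an ordinary allocation, nobody who can influence enrolment knows the next assignment, and no outcome in the trial affects it. The replacement rule weakens both conditions.

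First, an exacerbation occurs after randomisation and could depend on treatment. If it leads to replacement, events in one arm help decide how often that arm is refilled. Replacement is also optional, so it is settled case by case in consultation with an organisation whose team members may have seen the arm and the participant's data. Neither document says that those consulted must be blind.

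Second, the replacement's arm is fixed in advance. At the interim analysis, Protocol 7.4 limits access to randomisation numbers already assigned, which conceals future allocations. A number formed by adding 1000 to an assigned one escapes that safeguard, because whoever knows the first code knows the second.

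What is at stake is how far the leg press strength comparison, a primary endpoint analysed separately in small male and female cohorts, can be defended as free of sponsor influence on allocation.

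**Working it through.** **Step 1: does the plan need the rule to reach its target?** Inputs from Protocol 5.2 and 10.1.1: 20 evaluable per arm, about 20% loss, SD 10.9 for percentage change in strength, 90% interval.

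- Randomised per arm = 20 / (1 − 0.20) = 25, as stated.
- Half-width = t(0.95; 2n − 2) × SD × √(2/n). For n = 20: 5.81 (stated 5.8). For n = 10: 8.45 (stated 8.45).

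The plan's figures reproduce. The 25 per arm already carries the anticipated loss, so the precision target does not depend on replacement at that loss.

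**Step 2: what share would hold an inherited arm?** The documents give neither an expected number of replacements nor a split of the 20% between exacerbations and other withdrawals, so the rate replaced, r, is an assumption. With 100 participants initially randomised and one round of replacement, the number replaced is k = 100r and the share of those enrolled is k / (100 + k).

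| Assumed rate replaced | k | Share with inherited arm |
|---|---|---|
| 5% | 5 | 5/105 = 4.8% |
| 10% | 10 | 10/110 = 9.1% |
| 15% | 15 | 15/115 = 13.0% |
| 20% | 20 | 20/120 = 16.7% |
| 30% | 30 | 30/130 = 23.1% |

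None of these is a bound. If replacements at 20% were themselves replaced, the share would be 25/125 = 20%. If all 60 places between 100 and the approximate ceiling of 160 were used this way, it would be 60/160 = 37.5%, although Protocol 5.2 does not say that those places inherit an arm.

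**Step 3: how outcome-triggered refilling can act on arm sizes.** As an illustration within one sex, assume 10% of one arm and 30% of the other have exacerbations and all are replaced. The arms enrol 25 × 1.10 = 27.5 and 25 × 1.30 = 32.5, a ratio of 1 to 1.18. The inherited share is (2.5 + 7.5)/60 = 16.7%. The imbalance is modest, but outcomes produce it.

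**Step 4: who can know the replacement's arm beforehand?**

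- Sponsor members unblinded in-stream: yes, if they have seen the original participant's code.
- Sites: ordinarily no. Protocol 7.4 does allow emergency unblinding, and it allows expedited reports that identify treatment to be sent to investigators. A site that received such information and knew of the link would know the replacement's arm.

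**Step 5: effect of the change.** If replacements took the next unused schedule number, the inherited share would be 0%. The 25 per arm and the half-width of 5.8 would stand.

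**The case against.** The best defence is that the inherited code came from a randomisation schedule generated before the study, that participants and all site personnel are blinded, and that container numbers differ from randomisation numbers. Nothing gives the sponsor a say in which patient a site enrols next. A replacement's prognosis is therefore not ordinarily chosen with the arm in view. This stands. A reader might infer that the randomised comparison no longer protects against selection, or that replacements are allocated non-randomly, but the documents do not support that. The arm is inherited from a random draw, and selection of patients by arm is not shown.

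A reader might also take one sixth (20/120) as the number affected, or as a maximum. It is neither. The 20% in Protocol 5.2 combines exacerbations with other withdrawals, while 7.3 covers exacerbations only. The 25 per arm already absorbs that loss, and 5.2 allows extra enrolment for attrition only when losses exceed it. Likewise, a count of 20 replacements among 100 with Day 90 data would need every replacement to finish and no replaced participant to contribute. With the same 20% loss among replacements it is 16/96.

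Three more limits hold:

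- The text requires consultation with the sponsor. It does not say that the sponsor decides alone or that the person consulted is unblinded.
- SAP 12.7.1 is a reporting convention. It does not say that replacements for other withdrawals inherit an arm, so it is a mismatch to reconcile and not evidence of more inherited allocation.
- Replaced participants are not dropped from the primary analysis if they have a baseline and a qualifying post-baseline assessment.

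The defence does not answer the absence of any blinding requirement for the consultation. The SAP cancels the interim analysis, but it still describes the design as sponsor unblind and does not withdraw the in-stream review.

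**Conclusion.** The concern holds in a limited form. Protocol 7.3 sets up a discretionary replacement rule, triggered by an outcome, under which an unblinded party can influence which arm is refilled. It also makes the replacement's arm predictable to anyone who knows the original's, which includes a site only in the exceptional case that the arm was disclosed to it.

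The size cannot be fixed from the documents. On the assumption that 5% to 30% of 100 participants are replaced once, about 5% to 23% of those enrolled would hold an inherited arm. No bias in the strength estimate has been demonstrated or quantified. The rule is worth changing because it weakens the allocation, is not needed for the stated precision at the anticipated loss, and is cheap to remove.

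**What to change.** 1. Amend Protocol 7.3 so that every replacement receives the next unused number on the sex-specific randomisation schedule through the central system, and delete the 1000-plus numbering.
2. Have the decision to replace made by people blind to arm and outcome data. Base it on the pooled count of exacerbations and other early withdrawals that Protocol 5.2 already uses, and not on individual cases.
3. Reconcile Protocol 7.3, which covers exacerbations, with SAP 12.7.1, which covers any withdrawn subject. State one rule for who may be replaced and how the replacement is allocated.
4. If any inherited-arm replacements have already been enrolled, report their number by sex and arm, and add to the SAP a sensitivity analysis of leg press strength that excludes them.

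The cost is protocol and SAP wording, a setting in the randomisation system and, if step 4 applies, one further run of the primary model. The downside is that final arm sizes may differ by a few participants.

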7.4. Blinding

This will be a double blind (sponsor unblind) study and the following will apply.

- The investigator or treating physician may unblind a participant's treatment assignment **only in the case of an emergency** OR in the event of a serious medical condition when knowledge of the study treatment is essential for the appropriate clinical management or welfare of the participant as judged by the investigator.
- It is preferred (but not required) that the investigator first contacts the Medical Monitor or appropriate GSK study personnel to discuss options **before** unblinding the participant's treatment assignment.
- If GSK personnel are not contacted before the unblinding, the investigator must notify GSK as soon as possible after unblinding, but without revealing the treatment assignment of the unblinded participant, unless that information is important for the safety of participants currently in the study.
- The date and reason for the unblinding must be fully documented in the CRF

A participant will be withdrawn if the participant's treatment code is unblinded by the investigator or treating physician. The primary reason for discontinuation (the event or condition which led to the unblinding) will be recorded in the CRF.

- GSK's Global Clinical Safety and Pharmacovigilance (GCSP) staff may unblind the treatment assignment for any participant with an SAE. If the SAE requires that an expedited regulatory report be sent to one or more regulatory agencies, a copy of the report, identifying the participant's treatment assignment, may be sent to investigators in accordance with local regulations and/or GSK policy.
- Members of the GSK study team will be unblinded for in-stream data reviews and the interim analyses as appropriate. This may include the study statistician, programmers, physician project leader, Muscle Metabolism Discovery Performance Unit leader, safety review team and other decision makers. At the time of interim analysis, access to the randomization will be restricted to randomization numbers that have been assigned at the time of data cut-off.

7.5. Preparation/Handling/Storage/Accountability

1. The investigator or designee must confirm appropriate temperature conditions have been maintained during transit for all study treatment received and any discrepancies are reported and resolved before use of the study treatment.
2. Only participants enrolled in the study may receive study treatment and only authorized site staff may supply or administer study treatment. All study treatments must be stored in a secure, environmentally controlled, and monitored (manual or automated) area in accordance with the labeled storage conditions with access limited to the investigator and authorized site staff. Participants should be encouraged to store study treatment in a secure environment and follow directions for storage on the drug label.

3. The investigator, institution, or the head of the medical institution (where applicable) is responsible for study treatment accountability, reconciliation, and record maintenance (i.e., receipt, reconciliation, and final disposition records).
4. Further guidance and information for the final disposition of unused study treatment are provided in the Study Reference Manual.
- Under normal conditions of handling and administration, study treatment is not expected to pose significant safety risks to site staff. A Material Safety Data Sheet (MSDS)/equivalent document describing occupational hazards and recommended handling precautions either will be provided to the investigator, where this is required by local laws, or is available upon request from GSK.

7.6. Treatment Compliance

- When participants are dosed at the site, they will receive study treatment directly from the investigator or designee, under medical supervision. The date and time of each dose administered in the clinic will be recorded in the source documents. The dose of study treatment and study participant identification will be confirmed at the time of dosing by a member of the study site staff other than the person administering the study treatment.
- When participants self-administer study treatment(s) at home, compliance with GSK2881078 will be assessed through querying the participant during the site visits and documented in the source documents and CRF. A record of the number of GSK2881078 tablets dispensed to and taken by each participant must be maintained and reconciled with study treatment and compliance records. Treatment start and stop dates, including dates for treatment delays and/or dose reductions will also be recorded in the CRF.
- Compliance at each visit will be determined as follows:
$$(\# \text{ dispensed} - \# \text{ returned}) \times 100 / (\# \text{ days since last visit})$$
- Participants estimated to have taken less than 80% or more than 120% of study treatment capsules at two consecutive visits will be considered noncompliant. All attempts should be made to improve the participant's compliance in taking study treatment if the participant is continuing in the study.

